### **9.4. Analyses**

A formal SAP will be written and finalized prior to database lock. The SAP will detail the summaries and analyses to be performed.

- Primary endpoint:

The primary endpoint of the study is the Navio System assisted UKR revision rate at 2 years postoperatively. A one-sided 95% confidence interval for the revision [free] rate of the Navio System assisted UKR will be calculated using exact binomial methods. Non-inferiority, using a 7% non-inferiority margin will be declared if the lower bound of the confidence interval is  $>88.7\%$ . Time to occurrence of revision will also be analyzed using Kaplan-Meier survival analysis. Where appropriate, statistical modeling will be considered with prognostic and baseline factors adjusted for.

- Secondary endpoints:

Where appropriate, the secondary endpoints will be analyzed using either an ANOVA or Repeated Measures analysis, depending on whether a comparison between two time points or multiple time points is conducted. In each case, prognostic and baseline factors will be adjusted for. For endpoints where further analysis is not warranted, or not considered appropriate, tabulations detailing frequency distributions and/or summary statistics will be produced.

- Safety:

Numbers and types of AE, along with rates of AE types; with 95% confidence intervals for the rates (constructed using either exact binomial or asymptotic methods where appropriate) will be tabulated.

## 10. ETHICAL CONSIDERATIONS

### 10.1. Ethical Approval

In accordance with the Declaration of Helsinki and local regulations of the participating countries, sites must gain written IRB/EC approval prior to enrolling research participants in the study.

### 10.2. Protocol Amendments

Neither the Investigator nor the Sponsor will modify this protocol without mutual agreement. After agreement to initiate the modification, in the form of a protocol amendment, the Investigator agrees not to implement this modification until instructed to do so by the Sponsor. It will be necessary to obtain IRB/EC approval prior to implementation of any change in the protocol that may affect the scientific soundness or the rights, safety, or welfare of the subjects involved. Notification shall be submitted to the IRB/EC of the study site by the Investigator.

### 10.3. Informed Consent

Investigators must apply for the appropriate IRB/EC approvals on this study.

An IRB/EC waiver of informed consent for study participation should be requested for those subjects who meet eligibility criteria and have retrospectively completed a 2-year postoperative visit, are deceased, or are lost to follow-up/cannot be contacted, as per IRB/EC policy. If allowed, the informed consent waiver from the IRB/EC will allow for retrospective data collection from all subjects who have undergone Navio System assisted UKR, thereby eliminating selection bias. A copy of the waiver of informed consent will be placed in the subject file.

Subjects who meet eligibility criteria, are alive and have not completed a 2-year postoperative visit must sign an IRB/EC approved ICF according to ISO14155 guidelines, GCP guidelines and all applicable national regulations prior to any retrospective or prospective data collection. These subjects must be informed of the purpose of the study and the potential risks and benefits known or that can be reasonably predicted or expected as described in the written consent form. The subject shall have sufficient opportunity to consider participation in each phase of the study; a subject cannot be led to believe that they are waiving their rights as a subject or the liability of the Sponsor or Investigator. Subjects are then invited to sign and date the consent form, indicating their consent for participation in the retrospective and/or prospective phases of the study. The Investigator will retain the original copy of the signed consent form in the study files. A duplicate copy shall be provided to the subject.

### 10.4. Risk – Benefit Analysis

#### A. Study-Related Risks

**Possible risks that may occur as a result of study procedures are:**

- Subjects completing the prospective phase of the study will be asked to complete questionnaires, however, these are not interventional procedures and are not expected to add significant time.
- The prospective phase of the study involves the use of x-ray evaluation. X-ray exposure is cumulative over a lifetime and total exposure should be kept to a minimum. However, since the x-ray exposure when participating in the study is equivalent to the exposure the subject would receive if they chose not to participate in the study, there is no additional risk associated with this study.

- As a result of enrollment in the study, there could be a risk of loss of protected subject information confidentiality. All applicable confidentiality standards and data protection and privacy laws will be followed by the Sponsor to ensure that data collected is handled in confidence. Data will be coded and handled only by appropriately qualified and authorized personnel.

Risks related to the general surgical procedures are not considered here because these could be present regardless of participation into the study.

## **B. Study-Related Benefits**

Because the surgery and all the follow-up visits are the same as if the subject would not participate in this study, there are no additional medical benefits associated with participating in this study. The information gained from this study may help improve the treatment of people that need to undergo UKR.

## **11. MONITORING PROCEDURES**

### **11.1. Source Documentation**

Investigators are responsible for obtaining and maintaining complete subject health information in the medical record for each subject (source documents). Examples of source documents are hospital records, clinic and office charts, memoranda, dispensing records, subject questionnaires, clinic evaluation transcriptions, operative notes, x-rays, radiology reports, blood collection reports and shipment records, and research subject files. Members of the Investigator study site team will abstract data from source documents into study specific paper CRFs developed by the Sponsor.

As a minimum entry in the medical records, the PI shall ensure that clinical records are clearly marked to indicate that the subject is enrolled in a particular clinical study and if they completed per protocol or discontinued early and the reason.

### **11.2. Direct Access**

This study may be monitored by the Sponsor or a qualified person designated by the Sponsor. This qualified person could be an employee of the Sponsor or of a Contract Research Organization (CRO - Sponsor's agent).

The Investigator will provide the Sponsor, Sponsor's agents, IRB/EC and regulatory agencies with direct access to all source data/documents to permit study-related monitoring, audits, IRB/EC review, and regulatory inspections.

### **11.3. Site Qualification Visit**

A site qualification visit may be performed by the Sponsor or designee prior to the execution of a clinical agreement to ensure that all Investigators have the appropriate training, staff, facilities and resources to adequately conduct the study.

### **11.4. Prior to Study Initiation**

The Investigator must ensure the activities below are completed prior to the initiation of the study and provide supporting documentation to the Sponsor:

- **Clinical Study Agreement:** must be fully executed with the site and the Sponsor and any other appropriate party.
- **Documentation of Qualifications:** a current, signed and dated Curriculum Vitae (CV) for the Investigator and for all key members of investigator study site team listed on the Delegation of Authority Log must be submitted to the Sponsor prior to the study and updated as applicable to staff changes and confirmed at close out visit.
- **Conflict of Interest:** all participating Investigators are required by International Organization for Standardization (ISO) 14155 to provide details of conflict of interest (including financial, if applicable) according to local regulations. This information must be updated promptly by the Investigator and submitted to the Sponsor if any changes occur through the duration of the study and for one year following completion of the study.

#### **11.5. Site Initiation Visit**

A site initiation visit to provide training on the specifics of the study, site obligations and expectations of study conduct will be performed by the Sponsor or designee following execution of the Clinical Study Agreement and documented IRB/EC approval.

#### **11.6. Interim Monitoring Visits**

A clinical monitor, whether an employee of the Sponsor or its designee, has the obligation to follow this study closely. In doing so, the monitor will, in addition to maintaining necessary contact with the study site, visit the study sites at periodic intervals according to a schedule determined by the Sponsor. During these visits, the monitor will:

- verify informed consent process
- perform source data verification according to the Clinical Monitoring Plan
- verify that source documentation is complete and available
- ensure compliance with the protocol
- ensure all required study documentation is complete and available in Investigator Site File

#### **11.7. Sponsor Audits and Regulatory Inspection**

Quality assurance auditors, whether an employee of the Sponsor or its designee, may evaluate study conduct at the study sites. These parties must have access to any and all study reports and source documentation, regardless of location and format.

#### **11.8. Closeout Visit**

A study close-out visit will be performed by the Sponsor or designee to retrieve and account for all remaining clinical data and to resolve outstanding queries. During study close-out, the monitor will review investigator files to ensure required documents and records are on file, confirm the disposition of any other ancillary items used for the study, and review regulatory requirements regarding records retention and IRB/EC reporting requirements.

#### **11.9. Documentation of Monitoring Visits**

Activities associated with a monitoring visit will be documented by the monitor. This includes:

- monitor visit log on site

- a follow-up letter to the Investigator following each monitor visit summarizing the visit and detailing any site deficiencies and action items to clarify or address issues noted

#### **11.10. Data Handling and Record Keeping Requirements**

CRF will be supplied by the Sponsor. Subjects will be identified by a subject ID and subject code. Only the Investigator site will have the key to identify individual subjects.

The Investigator is responsible for the timely and accurate completion of CRF. All documents related to the study must be securely archived at the study site or in a central archive.

Data required according to this protocol are to be recorded on the CRF at the time of medical record review. Once a subject is enrolled, completed CRF should be sent to the Sponsor, either by fax or by e-mail, as soon as possible, and no later than 10 working days upon completion of the CRF.

#### **11.11. Data Recording and Record Retention**

Clinical research records shall be stored in a manner that ensures privacy, confidentiality, security and accessibility of the records both during and after the conduct of the study. The Investigator/Institution will take measures to prevent accidental or premature destruction of those documents. The Investigator must retain essential study documents for at least 2 years after the latest of the following: the date the study is terminated or completed or the date the documents are no longer needed to support a premarket approval application. If the Investigator needs to dispose of the documents, the Sponsor should be contacted for approval prior to disposal or destruction. For discontinued product, the essential documents will be retained until at least 2 years have elapsed since the formal discontinuation (via notification of the Food and Drug Administration [FDA] or other regulatory agency) of clinical development of the investigational product. The Investigator will retain these documents for a longer period if required by the applicable local laws.

If the responsible Investigator retires, relocates, or withdraws from responsibility of keeping the study records, custody must be transferred to a person who will accept the responsibility. The Sponsor must be notified in writing of the name and address of the new custodian. Under no circumstance shall the Investigator relocate or dispose of any study documents before having obtained written approval from the Sponsor.

### **12. DEVIATIONS FROM PROTOCOL**

A protocol deviation is an instance of failure, intentionally or unintentionally, to follow the requirements of the protocol. Protocol deviations include but are not limited to: deviations from inclusion/exclusion criteria, endpoint variable criteria, study visits outside the window, and GCP guidelines.

#### **12.1. Protocol Deviation Reporting Requirements**

Deviations must be reported to the Sponsor through the specially designed Protocol Deviation Log as soon as reasonably possible.

When protocol deviations affect the scientific soundness of the study or the rights, safety or welfare of the study subjects, the Investigator must also report protocol deviations to the IRB/EC of the study site. It is the responsibility of the Principal Investigator (PI) to inform the IRB/EC of the study site of the incident, per local requirements. The local IRB/EC should be consulted on protocol deviation reporting requirements.

Investigators and all study staff (staff at the site and at Sponsor) are responsible for ensuring adherence to study protocol. During the monitoring visits, the Sponsor representative will review all deviations with the Investigator. If a deviation is discovered outside of a monitoring visit, it should be evaluated via phone, email or letter. Appropriate measures to address the occurrence, additional monitoring visits, or audit of the study should be taken, which may include defining and implementing a Corrective and Preventive Action (CAPA).

### **13. Publication Policy**

The preparation and submission for publication of manuscripts containing the study results shall be in accordance with a process determined by the Clinical Trial Agreements between the study Sponsor and participating institutions. The publication or presentation of any study results shall comply with all applicable privacy laws, including, but not limited to the Health Insurance Portability and Accountability Act of 1996.

SAP	Statistical Analysis Plan
SF-12	Short Form 12 Health Survey Standard
TFL	Tables, Figures, and Listings
UADE	Unanticipated Adverse Device Effect(s)
UKR	Unicompartmental Knee Replacement
VR-12	Veterans RAND 12 Item

CONFIDENTIAL AND PROPRIETARY

This document contains information that is confidential and proprietary to Smith & Nephew PLC and Smith & Nephew, Inc. and is intended for use only by Smith & Nephew and its manufacturer. It shall not be reproduced or copied in whole or in part, nor shall the contents be disclosed by any means without prior written permission from Smith & Nephew, nor shall anyone make any use of it that is contrary to the expressed or implied wishes of Smith & Nephew.

Statistical Analysis Plan	 smith&nephew
A Retrospective Study of the NAVIO Robotic-assisted Surgical System	Number: 16-NPFS-11
	Version: Final 1.0, Jan 29, 2018
	Page: 6 of 25

2. Introduction

This statistical analysis plan (SAP) is written to specify the statistical analyses that would be carried out for study protocol 16-NPFS-11 in greater detail than the protocol. The statistical details provided herein would serve as guideline for the programming that would generate this study's tables, figures, and listings (TFLs).

The SAP is based on version 2.0 of the protocol dated 05 June 2017 and version 3.0 of the study's accompanying case report forms (CRFs).

3. Study Design

The NAVIO system is designed to assist surgeons in providing software-defined spatial boundaries for orientation and reference information to anatomical structures during orthopedic surgical procedures.

This study is a retrospective, multi-center, cohort study to be carried out on approximately 128 subjects enrolled at up to 10 investigational sites. These subjects would have previously undergone the NAVIO System-assisted Unicondylar Knee Replacement (UKR) for restoring either compartment of the knee that has been affected by any of the following conditions: (a) Non-inflammatory degenerative joint disease including osteoarthritis, traumatic arthritis, or avascular necrosis (b) Correction of functional deformity and (c) Treatment of fractures that are unmanageable using other techniques.

CONFIDENTIAL AND PROPRIETARY

This document contains information that is confidential and proprietary to Smith & Nephew PLC and Smith & Nephew, Inc. and is intended for use only by Smith & Nephew and its manufacturer. It shall not be reproduced or copied in whole or in part, nor shall the contents be disclosed by any means without prior written permission from Smith & Nephew, nor shall anyone make any use of it that is contrary to the expressed or implied wishes of Smith & Nephew.

Statistical Analysis Plan	 smith&nephew
A Retrospective Study of the NAVIO Robotic-assisted Surgical System	Number: 16-NPFS-11
	Version: Final 1.0, Jan 29, 2018
	Page: 7 of 25

Subjects enrolled would be followed-up for evaluation of safety and effectiveness of the device. Subjects would retrospectively be evaluated pre-operatively and operatively and prospectively at subsequent available post-operative follow-up visits for up to 2 years (24 months) or beyond. In order to evaluate the effectiveness of the NAVIO system-assisted investigational device, information on the revision rate (or survivorship) from a currently used device from an appropriate registry would be used as historical control. The historical control's revision (or survivorship) rate which was obtained from an orthopedic registry is specified in future sections of the SAP.

The study schematic displayed in Table 1 provides a succinct overview of the parameters evaluated within the study design.

CONFIDENTIAL AND PROPRIETARY

This document contains information that is confidential and proprietary to Smith & Nephew PLC and Smith & Nephew, Inc. and is intended for use only by Smith & Nephew and its manufacturer. It shall not be reproduced or copied in whole or in part, nor shall the contents be disclosed by any means without prior written permission from Smith & Nephew, nor shall anyone make any use of it that is contrary to the expressed or implied wishes of Smith & Nephew.

Statistical Analysis Plan	 smith&nephew
A Retrospective Study of the NAVIO Robotic-assisted Surgical System	Number: 16-NPFS-11 Version: Final 1.0, Jan 29, 2018 Page: 8 of 25

Table 1: Study schematic.

	Retrospective Data Collection ¹				Prospective Data Collection ²
	Screening and Enrollment	Pre-operative	Operative / Discharge	Follow-up	
Informed Consent	✓ ³				
Inclusion/Exclusion	✓				
Demographics/ Medical History		✓			
Operative and Discharge Data Collection			✓		
Implant Status ⁴				✓	✓
Knee Society Score (KSS)		✓		✓	✓
VR-12		✓		✓	✓
Radiographic Assessment		✓	✓	✓	✓
Adverse Event Assessment			✓	✓	✓
End of Study/Exit				✓*	✓

¹Given the retrospective-prospective study design, data will be collected to the extent it is available.

²Visit may occur in an office or remotely. If completed remotely (e.g. telephone call, mailing of subject questionnaires and/or any other means), secondary endpoint data will be collected to the extent possible.

³Informed consent/waiver of informed consent from the IRB/EC must be obtained prior to retrospective and prospective data collection.

⁴Subjects who have undergone a revision procedure of the study knee will be considered terminated from the study from the date of the revision. Study related data will not be collected following the date of the revision.

*if applicable

4. Study Objectives

4.1 Primary Objective

CONFIDENTIAL AND PROPRIETARY

This document contains information that is confidential and proprietary to Smith & Nephew PLC and Smith & Nephew, Inc. and is intended for use only by Smith & Nephew and its manufacturer. It shall not be reproduced or copied in whole or in part, nor shall the contents be disclosed by any means without prior written permission from Smith & Nephew, nor shall anyone make any use of it that is contrary to the expressed or implied wishes of Smith & Nephew.

Statistical Analysis Plan	smith&nephew
A Retrospective Study of the NAVIO Robotic-assisted Surgical System	Number: 16-NPFS-11
	Version: Final 1.0, Jan 29, 2018
	Page: 9 of 25

The primary objective of this study is to evaluate the 2-year safety and effectiveness of the NAVIO System's assisted implanted UKR in subjects aged ≥ 18 years.

5. Study Endpoints

5.1 Primary Endpoint

The NAVIO System assisted UKR implant survivorship (absence of device revision) at 2+ years (96 weeks) post-surgical implantation.

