5.2 Secondary Endpoints

Table 2 displays the visit windows for evaluation time points that would be used for summarizing the KSS and the VR-12 endpoints. Based on this, for situations in which two or more KSS or VR-12 observations present at a given visit, the observation closest to the upper range of the window would be selected for summary purposes for the visit.

Table 2. Summary of visit windows used for summarizing KSS and VR-12 endpoints

Month	Range of Days (windows) for Month Membership for follow-up post-surgical implantation
6 Months	≤ 182 days
12 Months	>182 to ≤ 365 days
18 Months	>365 to ≤ 548 days
24 Months	>548 to ≤ 730 days
30 Months	>730 to ≤ 913 days
36 Months	>913 to ≤ 1095 days

The secondary endpoints are as follows:

- Two-year (24 months) postoperative visit Knee Society Score (KSS).

CONFIDENTIAL AND PROPRIETARY

[figure not shown]
This document contains information that is confidential and proprietary to Smith & Nephew PLC and Smith & Nephew, Inc. and is intended for use only by Smith & Nephew and its manufacturer. It shall not be reproduced or copied in whole or in part, nor shall the contents be disclosed by any means without prior written permission from Smith & Nephew, nor shall anyone make any use of it that is contrary to the expressed or implied wishes of Smith & Nephew.

Statistical Analysis Plan	 Number: 16-NPFS-11 Version: Final 1.0, Jan 29, 2018 Page: 10 of 25
A Retrospective Study of the NAVIO Robotic-assisted Surgical System	

- Two year (24 months) post-operative visit VR-12 domain and sub-domain scores. These scores would encompass the individual domains of physical component score (PCS), mental component score (MCS) as well as the sub-domain scores within the PCS (physical functioning, role physical, bodily pain, and general health) and those within the MCS (vitality, social functioning, role emotional, and mental health).
- Anterior/Posterior and lateral radiographic assessments which include but not only restricted to the following:
 - Radiographic findings
 - Component orientation
 - Radiolucencies
 - Migration
 - Osteolysis
 - Stress shielding
 - Subsidence

CONFIDENTIAL AND PROPRIETARY

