6.1 Determination of Sample Size

The sample size obtained for study is based on the non-inferiority of the percent of revision-free survival expected to be obtained at 2 years in the study, π to one obtained from existing literature, π_0 . The Australian Orthopaedic Association National Joint Replacement Registry 2015 Annual Report (1) indicates that the revision-free survival at 2-years is 95.7%.

Using a non-inferiority margin, δ of 7%, a sample size of 115 subjects would provide at least 80% power at the 5% significance level using the exact binomial method. To allow for a 10% attrition and drop-out rate, a total of approximately 128 subjects would be enrolled into the study.

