7.3 Handling of Missing, Incomplete and Repeat Data

Not all subjects enrolled into this study would complete the study. Subjects who die or discontinue without a revision would have their data censored on their date of death/discontinuation. Subjects who do not have a revision by the end of the study would have their data censored at their last known study visit date.

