7.10 Analysis of Primary Endpoint

CONFIDENTIAL AND PROPRIETARY

This document contains information that is confidential and proprietary to Smith & Nephew PLC and Smith & Nephew, Inc. and is intended for use only by Smith & Nephew and its manufacturer. It shall not be reproduced or copied in whole or in part, nor shall the contents be disclosed by any means without prior written permission from Smith & Nephew, nor shall anyone make any use of it that is contrary to the expressed or implied wishes of Smith & Nephew.

Statistical Analysis Plan	smith&nephew
A Retrospective Study of the NAVIO Robotic-assisted Surgical System	Number: 16-NPFS-11
	Version: Final 1.0, Jan 29, 2018
	Page: 20 of 25

For the primary endpoint, cumulative proportion (or percentage) of subjects with implant survivorship at 2+ years (96 weeks), the following is the hypothesis would be performed:

H_0 (null): $S(t) = \pi \leq (\pi_0 - \delta)$ versus

H_a (alternate): $S(t) = \pi > (\pi_0 - \delta)$,

where π = expected percentage of subjects with implant survivorship at 2 years, π_0 = historical control implant survivorship (95.7%) and δ = margin of non-inferiority (7%).

Because not all subjects would be fully evaluated through study completion, the Kaplan-Meier product limit survival estimate would be used to estimate implant survivorship, $S(t)$ where $S(t)$ is the proportion of subjects at time t , without a device revision. Time to implant revision would be the endpoint of interest in the determination of implant survivorship.

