Cumulative proportions of subjects with implant survivorship at 2 years would be calculated and displayed accordingly. Subjects who complete the study without a revision would be censored at their last known date in the study. A subject who prematurely discontinues from study as a result of death or for any other reason would be censored at the date this event occurred. A subject who is lost to follow-up would be censored at the last known contact date. The Kaplan-Meier estimate for implant survivorship would be presented with the corresponding two-sided 95% Confidence Intervals (CIs). This study's hypothesis test would only be carried out at the end of the study at 2+ years (96 weeks). From this test, if the lower limit (LL) of the 95% two-sided CI for $S(t = 2 \text{ years}) > (\pi_0 - \delta) = 88.7\%$, then H_0 will be rejected in favor of H_a (i.e. demonstration of non-inferiority of the investigational device) otherwise H_0 would not be rejected. Kaplan-Meier estimates for implant survivorship would also be non-inferentially estimated at the intermediate time points of 6 months (24 weeks), 1 year (48 weeks), and at 18 months (72 weeks) as well as subsequently at 30 months (120 weeks).

The primary endpoint would be analyzed using the safety population as the primary analysis population while the per protocol population would be used for sensitivity analysis.

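### The SAP sets its only hypothesis test at both 96 weeks (day 672) and 2 years (day 730); using 96 weeks could only help the device against a 2-year benchmark

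*SAP*

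**What the plan says.** **Places that give 96 weeks.** SAP 5.1 defines survivorship "at 2+ years (96 weeks) post-surgical implantation". The lead-in to the hypotheses in SAP 7.10 concerns the "cumulative proportion (or percentage) of subjects with implant survivorship at 2+ years (96 weeks". Later in 7.10 the study's "hypothesis test would only be carried out at the end of the study at 2+ years (96 weeks".

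**Places that give 2 years.** Within SAP 7.10, π is the "expected percentage of subjects with implant survivorship at 2 years", and "Cumulative proportions of subjects with implant survivorship at 2 years would be calculated and displayed accordingly". The rejection rule compares the lower limit of the two-sided 95% interval for S at t = 2 years with 88.7%. SAP 6.1 takes its control from a registry report that "indicates that the revision-free survival at 2-years is 95.7"%. The primary endpoint in Protocol 2.1 is at 2 years and has no week count.

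**Related text.** SAP Table 2 (KSS and VR-12 windows) defines month 24 as ">548 to ≤ 730 days". SAP 7.10 labels its descriptive estimates at 6, 12, 18 and 30 months as 24, 48, 72 and 120 weeks. SAP 7.15, which lists departures from the protocol, declares no change of time point.

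**The concern.** A Kaplan-Meier estimate has to be read at one time. The SAP gives two, 58 days apart, for its only confirmatory test, and two programmers could each follow it faithfully and evaluate the test on different days.

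The discrepancy has a direction. The benchmark counts failures over the full 2 years. A study estimate read at day 672 omits any revision on days 673 to 730. A survival curve cannot rise, so the earlier reading is either equal or more favourable. Near the decision limit, one revision in those 58 days can settle the verdict. If the time is still open when results are known, the choice between the two readings could be made with the answer in view.

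**Working it through.** **1. The plan's own sample size.** Inputs from SAP 6.1: benchmark 95.7%, margin 7 points, limit 95.7 − 7 = 88.7%, 5% level, exact binomial. With n = 115 and a one-sided 5% test, success means at most 7 revisions; exact error 4.5%, power 87.7%. 115/0.90 = 127.8, rounded up to 128. The stated figures are reproduced. SAP 7.10 uses the lower limit of a two-sided 95% interval. With exact limits and n = 115 that allows at most 6 revisions, with error 2.0% and power 77.4%.

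**2. The time gap.** 96 × 7 = 672 days; 672/30.4375 = 22.1 months; 730 − 672 = 58 days, or 7.9% of the 2-year period. All the week labels use four weeks per month (6 × 4 = 24, 12 × 4 = 48, 18 × 4 = 72, 24 × 4 = 96, 30 × 4 = 120), so a conversion slip is the likely cause.

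**3. Shift in the estimand.** The documents give no hazard shape. I assume a Weibull: S(672) = S(730)^((672/730)^k), with k = 1 (constant hazard) as the main case.

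| True S(730) | k = 0.5 | k = 1 | k = 2 |
|---|---|---|---|
| 88.7% | 89.13% (+0.43) | 89.55% (+0.85) | 90.34% (+1.64) |
| 95.7% | 95.87% (+0.17) | 96.03% (+0.33) | 96.34% (+0.64) |

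**4. False non-inferiority at a true 2-year rate of 88.7%.** The SAP does not name the interval type, so several are shown. The exact rule is P(X ≤ 6) with n = 115. The Kaplan-Meier rows come from 40,000 simulated studies with 128 enrolled, 10% uniform dropout by day 730 and everyone else followed past day 730.

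| Two-sided 95% limit | Read at day 730 | Read at day 672, k = 1 | k = 0.5 to 2 |
|---|---|---|---|
| Exact binomial | 2.0% | 3.75% | 2.8% to 6.4% |
| Kaplan-Meier, log-log | 1.3% | 2.5% | 1.8% to 4.8% |
| Kaplan-Meier, linear | 5.7% | 9.7% | 6.8% to 15% |

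**5. How often the verdict changes** (k = 1, same simulation).

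| True S(730) | 92% | 93% | 94% | 95% | 95.7% |
|---|---|---|---|---|---|
| Log-log | 6.0% | 7.4% | 8.3% | 7.7% | 6.0% |
| Linear | 9.5% | 9.5% | 7.9% | 4.8% | 2.8% |

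Every change was towards non-inferiority; none went the other way.

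**6. A concrete case.** Take 115 knees, all followed past day 730, with 6 revised by day 672 and a seventh on day 700. Lower limits against 88.7%:

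| Limit | 6 revisions | 7 revisions | 8 revisions |
|---|---|---|---|
| Log-log, two-sided 95% | 88.76% | 87.66% | 86.57% |
| Exact, two-sided 95% | 88.99% | 87.86% | 86.75% |
| Linear, two-sided 95% | 90.72% | 89.54% | 88.39% |

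Under log-log or exact limits the day-672 reading passes and the day-730 reading fails. Under linear limits the same change happens one revision later, between 7 and 8.

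**The case against.** The strongest reply is that the operative text already means 2 years. The rejection rule, π, the displayed estimate, the sample size and the benchmark all say so, as does the protocol. In the sentence about the test, 96 weeks could be read as describing when the test is performed, with the next sentence fixing t. Twenty-two months cannot be two years or more, and SAP 7.15 declares no change. On this view the fault is a label. This has force as evidence of intent, and it is why day 730 is the right correction. It does not remove the conflict: 96 weeks is the only count in weeks or days attached to the primary endpoint, it appears three times, and one of those is the endpoint definition.

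A second reply is that the numbers depend on the interval type. That stands in part. A seventh revision does not change the verdict under linear limits, nor under the protocol's one-sided 95% exact limit (88.87% at 7 revisions). The change then comes at the eighth, where that exact limit is 87.8%. The interval type also moves the error rate at day 730 (1.3% against 5.7%) more than the time point does under log-log limits, and the 2.5% log-log figure at day 672 is no more than the nominal one-sided level. The unspecified interval type is a separate issue.

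A third reply is that the effect is small at the planned rate: 0.33 points, about 0.4 revisions in 115. That is correct.

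**Conclusion.** The concern holds and should be fixed before database lock. The conflict is in the SAP text and needs no assumption. Nor does the direction of the estimate: S(672) is never below S(730), and the two are equal if no revision falls in the 58 days. That the lower limit moves the same way was checked by simulation.

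The size does rest on assumptions about hazard shape, dropout timing and interval type. The shift is small at the benchmark. At the 88.7% limit it is 0.85 points (0.43 to 1.64). With a constant hazard, that nearly doubles the false non-inferiority rate under exact or log-log limits and raises it by about 70% under linear limits (9.7/5.7 = 1.7). If the programmer uses 2 years, nothing is lost, but the SAP does not ensure that.

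**What to change.** Replace 96 weeks with day 730 (24 months) in SAP 5.1 and at both places in 7.10, and state that S(t) and its confidence interval are evaluated at t = 730 days. Relabelling the 24-, 48-, 72- and 120-week estimates in days is optional, because they are descriptive.

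Also report the number at risk at day 730 and the number censored on days 639 to 729. The protocol accepts the 2-year visit up to 3 months early, and SAP 7.3 states: "Subjects who do not have a revision by the end of the study would have their data censored at their last known study visit date". Early attenders therefore leave the risk set before day 730. This follows from the visit window and would remain after the label is corrected.

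The change costs a few words and one programming constant. Simulated power at a true 95.7% falls from 79% at day 672 to 73% at day 730 under log-log limits, and from 94% to 91% under linear limits. That drop is mainly the loss of an advantage the comparison should not have. If half of the visits fall on days 639 to 730 (an assumption), power is 70% (log-log) or 89% (linear), and the mean number at risk at day 730 falls from about 110 to about 55 of 128.
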